## Lay Summary of Proposed Research

Lay Summary of Proposed Research

Individuals with Late Life Depression (LLD) often have cognitive problems, particularly problems with memory, attention, and problem solving, all of which contribute to antidepressant non-response. Our group and others have shown that decreased thinking speed is the central cause of functional problems in patients with LLD. Similarly, decreased walking speed is associated with depression and carries additional risk for falls, hospitalization, and death. Available evidence suggests that declining functionality in the brain's dopamine system contributes to age-related cognitive and motor slowing. The central hypothesis of this R61/R33 Phased Innovation Award is that by enhancing dopamine functioning in the brain and improving cognitive and motor slowing, administration of carbidopa/levodopa (L-DOPA) will improve depressive symptoms in older adults.

This IRB protocol pertains to the R33 Phase of this grant proposal (R61 Phase was approved under IRB #7270). In the R33 Phase 90 adults aged > 60 years with (1) a DSM 5 depressive disorder, (2) significant depressive symptoms, and (3) decreased thinking or walking speed will receive 8 weeks of treatment with

L-DOPA up to 450mg. We will test whether L-DOPA increases brain dopamine release using neuroimaging and whether it speeds up thinking and walking speed. Data collected in the proposed studies may help identify a new treatment for LLD, which could have large public health ramifications given the prevalence, frequent treatment resistance, and chronicity characteristic of LLD. This project also will elucidate the neurobiology of slowing at molecular, structural, and functional levels of analysis, increasing our understanding of the interplay between these aging-associated processes and the pathophysiologic changes underlying late life neuropsychiatric disorders. Exploring patient characteristics that predict response to L-DOPA may provide useful information to guide differential therapeutics and develop personalized medicine for LLD.

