## Specific Aims and Hypotheses

### Specific Aims and Hypotheses

We hypothesize that treatment with levodopa (L-DOPA) will improve depressive symptoms in LLD by enhancing striatal dopamine release and improving cognitive/motor slowing. In the R33 Phase, 90 adults aged > 60 years with (1) a DSM 5 depressive disorder, (2) significant depressive symptoms (CES-D > 10), and (3) decreased processing speed (0.5 SD below age-adjusted norms on the Digit Symbol Test or Trails A) or decreased gait speed (average walking speed over 15' course < 1m/s) will be receive 8 weeks of treatment with LDOPA 450mg. Subjects will be tested for engagement of molecular target by determining whether subacute (8 week) treatment with L-DOPA displaces [C]-raclopride on positron emission tomography (PET).

R33 Phase.

Aim 1: To determine whether L-DOPA improves depressive symptoms in older adults.

Hypothesis 1: Compared to placebo, L-DOPA administration will result in greater improvements in depressive symptoms (as measured by HRSD scores).

Hypothesis 2: Greater post-L-DOPA decreases in [C]-raclopride BP and increases in processing/gait speed will be associated with greater depressive symptom improvement.

Exploratory aims: To explore the role of inflammatory markers and Catechol-O-methyl-transferase (COMT) genotype in moderating L-DOPA induced changes in slowing and depressive symptoms.

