**Inclusion/Exclusion Criteria**

Name the subject group/sub sample

Patients

Create or insert table to describe the inclusion criteria and methods to ascertain them

Criterion	Method of Ascertainment
1. Age >59 years	1. Interview
2. DSM 5 non-psychotic Major Depressive Disorder, Dysthymia, or Depression Not Otherwise Specified	2. Clinical interview and SCID
3. Center for Epidemiological Studies Depression (CES-D) Rating Scale >9	3. CES-D
4. decreased processing speed (defined as performance > 0.5SD below age-adjusted norms on Digit Symbol Substitution Test or Trail Making Test Part A) OR decreased gait speed (defined as average walking speed over 15’ course < 1m/s)	4. Digit Symbol Substitution Test, Trails A, timing of walking speed
5. willing to and capable of providing informed consent and complying with study procedures	5. Clinical interview
6. Alternative standard treatments for MDD, Dysthymia, or Depression NOS (e.g., antidepressant medication or psychotherapy) have been discussed and the individual agrees to be involved in an experimental treatment.	6. Clinical interview

Create or insert table to describe the exclusion criteria and methods to ascertain them

Criterion	Method of Ascertainment
-----------	-------------------------

1. diagnosis of substance abuse or dependence (excluding Tobacco Use Disorder) within the past 12 months

1. Clinical interview and SCID

2. history of or current psychosis, psychotic disorder, mania, or bipolar disorder

2. Clinical interview and SCID

3. diagnosis of probable Alzheimer's Disease, Vascular Dementia, or PD

3. Clinical interview, MMSE for AD and VD. PD will be ruled out by satisfying (1) and (2) and (3 or 4) below:

(1) patient gives no history of PD during clinical interview

(2) patient's primary doctor gives no history of PD

(3) there are no signs of PD on physical exam in the LLDC

(e.g., absence of asymmetric resting tremor, decreased arm swing, soft voice, decreased facial expression, difficulty rising from chair, dystonia)

(4) If a patient does have one or more signs of possible PD on exam as per (3), [name] (study neurologist)

will come examine the patient and comment on whether PD can be ruled out or whether PD is possible and patient needs further neurologic work up.

4. Mini Mental Status Exam (MMSE) < 25

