4. If subjects are eligible for the study after review of their processing speed and gait speed and decide to participate by signing informed consent, then they will complete the remainder of the baseline assessment. This includes recording of each subject's chief complaint, referral source, age of onset of mood and/or cognitive decline, number prior depressive episodes, age, sex, marital status, race and ethnicity, years of education, employment status and income, years of education, family history. We also will document medical history, physical exam, urine drug screen, CBC, chemistries and electrolytes, thyroid profile, vitamin B12 and folate levels, urine analysis, and ECG. Vital signs will be measured at baseline and monitored weekly throughout the study. The Cumulative Illness Rating Scale-Geriatric (CIRS-G) (112) will be filled out at baseline to measure chronic medical illness burden. Subjects' current physical pain will be assessed weekly using a 100mm Pain Visual Analog Scale (VAS) and used as a covariate in analyses of gait speed (113).

5. Baseline markers of inflammatory status will be added to the serum assessments detailed above, including C-reactive protein (CRP), IL-6, and Tumor Necrosis Factor  $\alpha$  (TNF $\alpha$ ). The rationale for inflammatory marker measurement is evidence that dopaminergic dysfunction in older adults may be caused by the chronic, low-grade inflammatory process concomitant with aging ("inflammaging") (151). Pro-inflammatory cytokines such as IL-6 may reduce dopaminergic transmission in multiple ways, including decreasing dopamine synthesis by limiting tetrahydrobiopterin (BH4) availability, impairing vesicular release of dopamine in presynaptic neurons by decreasing expression of vesicular monoamine transporter 2 (VMAT2), increasing DAT reuptake of synaptic neurotransmitter, and decreasing glutamate-dependent dopamine signaling (152).

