### Assessments

21. Subjects are expected to have a screening/evaluation visit, pre-treatment PET/MRI scanning day(s) (for those receiving imaging), and weekly visits from Week 0-8.

22. The following measures will be collected weekly throughout the study: 24-item HRSD, CGI Severity and Improvement, Structured Pill Count Interview, Unified Parkinson's Disease Rating Scale (UPDRS) (questions 32 and 33 will be used in this study to assess the duration and disability of dyskinesias caused by L-DOPA), Treatment Emergent Side Effect Scale, and Inventory of Depressive Symptoms—Self Report (IDS-SR).

23. In addition, baseline processing and gait speed assessments will be repeated after **Weeks 1, 2, 5, and 8** at 1pm to control for time of day effects and the duration since the last morning L-DOPA dose (anticipated to be 4 hours). Processing speed will be assessed using the Digit Symbol test from the Wechsler Adult Intelligence Scale-III (WAISIII) (119) and the Pattern and Letter Comparison tests (120). These tests are all reliable and valid, with moderate to high loadings on the latent speed factor. A latent factor (and subsequent factor score) will be extracted from the 3-test battery pre- and post-treatment and used as the main outcome in the R61. By extracting a latent factor and factor loadings we will utilize a more pure measure of processing speed than if we used the raw scores from an individual test or a sum total score from the three raw scores combined (121-124).

24. Gait will be assessed as both a single and dual task (ST, DT) on a Gaitrite walkway system in the LLDC. For the ST, patients are instructed to walk at their usual or normal speed over the walking course. For the DT, patients are instructed to walk at their usual pace while simultaneously verbally listing as many animals as possible (fluency DT). In addition, a counting DT will be used in which patients are instructed to walk at their usual pace while simultaneously performing serial subtractions by threes starting at 100 (125). Patients will start and end at a point 2 meters from beginning of the course to eliminate acceleration and deceleration effects. Each ST and DT will be assessed two times with the average used in the analyses.

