Analyses for Aim 3: Aim 3.1: To determine whether L-DOPA administration results in greater improvements in depressive symptoms on the HRSD, a longitudinal mixed effects model will be used to analyze group differences using SAS Proc Mixed Version 9.3. The change in 24-item HRSD from baseline will be analyzed as a function of time, treatment group, the interaction between time and treatment, and baseline HRSD. Contrasts of mean difference in HRSD at each week will be formed and tested. Aim 3.2: To determine whether greater increases in processing and gait speed are associated with greater HRSD improvement, change scores from baseline to 8 weeks will be calculated for both processing and gait speed. Pearson correlation among all change scores, including change in HRSD will be examined, and two-sample t-tests will be used to assess treatment group differences. Multivariate linear regression models will be fit with change in HRSD as the outcome predicted by treatment, processing and gait speed change scores, and baseline values of processing and gait speed.

Exploratory aims: Inflammatory markers and COMT genotype will be tested as moderators of the L-DOPA effect on HRSD change by including their interactions with treatment in the Aim 3 analyses.

Power analysis: Aim 3.1: With N=45 per treatment group, and assuming a drop out of 15%, using two-sided test with $\alpha=0.05$, we have >80% power to detect treatment group differences with ES = 0.60 or greater. Given expected SD=5 points based on similar previously conducted studies in the LLDRRC, this ES would correspond to a change in HRSD of 3 points, which is smaller than the 4 point change considered meaningful. Aim 3.2: With N=90, assuming a drop out of 15%, we would be able to detect correlations >0.31. Thus, we have adequate power to detect a moderate to large correlations between change in HRSD and change in processing and gait speed.

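### The Aim 3.2 t-tests on speed change leave out baseline speed and the pain covariate that the protocol states for gait analyses

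*SAP*

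**What the plan says.** In the SAP, under Analyses for Aim 3, Aim 3.2 says that "change scores from baseline to 8 weeks will be calculated for both processing and gait speed". It then correlates all change scores, HRSD included, and adds that "two-sample t-tests will be used to assess treatment group differences". Its only model with covariates has "change in HRSD as the outcome predicted by treatment, processing and gait speed change scores, and baseline values of processing and gait speed". That model adjusts for baseline speed, but it explains HRSD change and does not estimate the effect of treatment on speed. Aim 3.1, by comparison, includes baseline HRSD in its mixed model.

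The protocol (Study Procedures, item 4) has the weekly "Pain Visual Analog Scale (VAS) and used as a covariate in analyses of gait speed", and Assessment Instruments repeats this. Neither part of the SAP mentions pain.

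On the role of speed, Hypothesis 2 in the protocol's Specific Aims is that "increases in processing/gait speed will be associated with greater depressive symptom improvement". The Lay Summary goes further: "We will test whether L-DOPA increases brain dopamine release using neuroimaging and whether it speeds up thinking and walking speed".

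**The concern.** There are two separate problems.

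- **Baseline.** Subtracting the baseline value is not the same as adjusting for it. When the two visits are imperfectly correlated, a raw change score usually carries more noise than a baseline-adjusted comparison. The SAP adjusts for baseline in its HRSD models but not here. The Overview's check for chance imbalance is worded for primary outcome measures, so it does not clearly reach speed.
- **Pain.** A two-sample t-test has no place for a covariate. An analyst who follows the SAP on gait departs from the protocol, and an analyst who follows the protocol departs from the SAP.

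At stake is the precision and traceability of the SAP's one between-arm analysis of speed. The HRSD comparison in Aim 3.1 is not affected.

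**Working it through.** **The plan's own figure.** The only number stated for Aim 3.2 is a detectable correlation above 0.31, with N=90 and 15% dropout. No power level is given, so I take 80%, as in Aim 3.1. By Fisher's z, r = tanh((1.960 + 0.842)/√(n − 3)). With 90 × 0.85 = 76.5, this gives 0.317 at n = 76 and 0.315 at n = 77. The stated figure reproduces to rounding. It concerns the correlation; no power is stated for the t-tests.

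**Inputs for the comparison of methods.**

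- From the SAP: 45 per arm, 15% dropout (45 × 0.85 = 38.25, taken as 38) and two-sided 0.05.
- Assumed, because the documents give no speed SD, effect size or correlation: an effect of 0.5 of the Week 8 SD; ρ, the baseline-to-Week-8 correlation; and v, the baseline variance divided by the Week 8 variance. Values of v below 1 are plausible because entry selects partly on low speed (performance "below age-adjusted norms on Digit Symbol Substitution Test or Trail Making Test Part A", or slow gait).

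**Formulas, in units of the Week 8 SD.**

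- SD of change = √(1 + v − 2ρ√v), with 2n − 2 degrees of freedom.
- SD after baseline adjustment = √(1 − ρ²), with 2n − 3 degrees of freedom.
- Noncentrality = 0.5 / (SD × √(2/38)). Power comes from the noncentral t distribution.

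Example at ρ = 0.5, v = 1: SD of change is 1.000 and noncentrality is 0.5/0.2294 = 2.18, giving 57.6% power. Adjusted SD is 0.866 and noncentrality is 2.52, giving 70.0%.

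| ρ | v = 1: t-test v ANCOVA | v = 0.75 | v = 0.5 |
|---|---|---|---|
| 0.3 | 44% v 62% | 49% v 62% | 55% v 62% |
| 0.5 | 58% v 70% | 63% v 70% | 68% v 70% |
| 0.6 | 67% v 77% | 72% v 77% | 76% v 77% |
| 0.7 | 79% v 85% | 83% v 85% | 85% v 85% |
| 0.8 | 93% v 95% | 95% v 95% | 94% v 95% |
| 0.9 | above 99% for both | above 99% for both | above 99% for both |

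At v = 1 the ratio of the two variances is (1 + ρ)/2: 0.65 at ρ = 0.3, 0.75 at 0.5, 0.85 at 0.7 and 0.95 at 0.9.

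The protocol's 68 required completers would give 34 per arm. At v = 1 the figures are then 53% v 65% at ρ = 0.5 and 75% v 81% at ρ = 0.7, so the pattern is the same.

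The formula ignores the small cost of chance baseline imbalance. In a simulation of 40,000 trials per cell that allowed for it (38 per arm), ANCOVA power ran up to about 1 point below the formula. At v = 0.5 and ρ = 0.7, ANCOVA came out slightly behind the t-test (84.8% v 85.4%). With no true effect (ρ = 0.6, v = 1 and 0.75), the t-test and ANCOVA with and without pain all rejected 4.8% to 5.2% of the time.

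**Pain.** No arithmetic is needed here. The protocol states twice that pain is a covariate in gait analyses. The SAP's between-arm test of gait admits no covariate, and pain appears nowhere in the SAP. Both cannot be followed. The protocol also does not say which of the weekly pain scores is meant.

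**The case against.** The strongest reply has four parts.

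- **The t-test is legitimate.** This stands. A reader might infer that the comparison is biased or invalid; under randomisation it is neither. No passage promises ANCOVA for speed, so the baseline point is about precision and contradicts nothing.
- **The comparison is secondary and partly inferred.** This also stands. The clause names no variable, the stated purpose of Aim 3.2 is association with HRSD change, and the hypotheses include no arm difference in speed. But the change scores are defined just before the clause, and if HRSD change is meant as well, the speed scores are still included. The Lay Summary does say that the effect on speed will be tested.
- **The pain sentence may be left over from the earlier R61 phase.** This is possible. The Assessment Instruments list still describes the HRSD in R61 terms, and Assessments item 23 has the speed factor "extracted from the 3-test battery pre- and post-treatment and used as the main outcome in the R61". Study Procedures item 4 is nevertheless current text. If it is a leftover, the remedy changes but the mismatch remains.
- **The mismatch should not be stretched.** A reader might infer that the regression on HRSD change must also contain pain. The protocol's words concern analyses of gait speed and do not clearly cover a model in which gait change is one predictor of another outcome. A reader might also infer that the analysis would be chosen once results are known. The documents do not show this: the SAP names a t-test in advance, and nothing says when the two texts would be reconciled.

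**Conclusion.** The point holds as a modest one, worth considering. The SAP's comparison of arms on speed change forgoes an adjustment that the data already allow, and for gait it cannot follow the protocol's statement on pain.

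The mismatch rests on the text alone. The size of the precision gain rests wholly on assumed inputs. With equal variances it runs from 17 points of power at a correlation of 0.3 (44.4% v 61.6%) through 12 at 0.5 and 6 at 0.7 to nothing material at 0.9. If baseline variance is 75% of the Week 8 variance, the gain at 0.5 falls to 7 points (63% v 70%). If it is 50%, the gain is about nil, or a loss of under 1 point, at correlations of 0.6 or more. These are illustrations over a range and do not bound the true gain.

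**What to change.** In SAP Aim 3.2, state that the arms are compared on Week 8 change by ANCOVA with treatment and baseline value as terms, for each speed measure. For gait, add baseline pain VAS. The baseline score is suggested because pain measured after randomisation could itself be affected by treatment. If the pain sentence is a carry-over from the R61 phase and is no longer intended, amend Study Procedures item 4 and Assessment Instruments instead, so that protocol and SAP agree.

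The cost is SAP wording and one or two degrees of freedom. Baseline speed and weekly pain are already collected, so no new data are needed. The sponsor should accept that ANCOVA may gain nothing, or lose a fraction of a point of power, if baseline variance turns out to be much smaller than Week 8 variance.

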Statistical Analysis Plan

Targeting Dopaminergic Mechanisms of Slowing to Improve Late-Life Depression

IRB #7733

NCT #03761030

Date: 07/24/15

Overview: All variables at all time points will be examined for illegitimate values, outliers, and inconsistencies. The distribution of demographic variables and baseline clinical characteristics will be examined and described across the two randomized patient groups (N=45 each) in terms of means, standard deviations, proportions, and 95% confidence intervals. Indications of inequality between groups in specific features (despite randomization) will trigger examination of whether differences in primary outcome measures can be attributed to an imbalance in group assignment. Intent-to-treat will be used for analyses including all participants who are randomized and have at least one post-baseline HRSD score. Tests will be two-sided and statistical significance determined at p-value < 0.05.

Missing data: We will make every effort to obtain all data. The longitudinal mixed modeling described below is valid if missing data are missing at random (MAR). MAR assumptions cannot be verified. A 2010 national expert panel (166) recommended sensitivity analyses for the impact of missing data via pattern mixture models (167), which we will conduct (e.g., by investigating robustness of results to perturbations of assumed values for missing data within clinically plausible ranges).

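### The Aim 3.2 regression of HRSD change omits baseline HRSD, which costs some precision and can bias the speed slopes in either direction; add it, and keep the planned model as a sensitivity analysis

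*SAP*

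**What the plan says.** The SAP (Analyses for Aim 3) models HRSD change twice.

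- **Aim 3.1**, the longitudinal mixed model: change in the 24-item HRSD "will be analyzed as a function of time, treatment group, the interaction between time and treatment, and baseline HRSD".
- **Aim 3.2**, the regression for the speed part of Hypothesis 2: "Multivariate linear regression models will be fit with change in HRSD as the outcome predicted by treatment, processing and gait speed change scores". The only other covariates it lists are the starting levels of those two speed measures.

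Aim 3.2 also has an unadjusted part: "Pearson correlation among all change scores, including change in HRSD will be examined". Its power statement rests on those raw correlations: "With N=90, assuming a drop out of 15%, we would be able to detect correlations >0.31". The general test rule is in the SAP Overview: "Tests will be two-sided and statistical significance determined at p-value < 0.05".

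No other part of the SAP or protocol adds baseline HRSD to the Aim 3.2 regression. The Overview's check for baseline inequality compares the randomized groups, so it does not bear on a slope for speed change.

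**The concern.** The regression adjusts for the starting values of both predictors but not of the outcome, and the SAP does not say why the covariate used in Aim 3.1 is dropped. A change score usually depends on its starting value, through regression to the mean and room to fall. Leaving baseline HRSD out puts that variation into the residual.

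There is also a question of bias. Speed change is observed after randomization and is not assigned, so randomization protects the treatment comparison but not the speed-to-mood slope. If starting severity also predicts how much speed changes, the slope partly reflects starting severity. Two features of the protocol make this plausible. Entry requires HRSD below 25 with no stated lower HRSD limit (Inclusion/Exclusion Criteria; Study Procedures), so severity may vary considerably. The Background section also describes a two-way link between depressive symptoms and gait speed.

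At stake is the one stated Aim 3.2 analysis that relates speed change to mood change with treatment held constant.

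**Working it through.** **Inputs from the SAP.** N = 90, 45 per arm; 15% dropout, so 90 × 0.85 = 76.5, taken as 76 completers; two-sided 0.05. The 80% power is stated for Aim 3.1 and assumed to carry over to Aim 3.2.

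**The plan's own figure.** By Fisher z, r = tanh[(1.960 + 0.842)/√(76 − 3)] = tanh(0.328) = 0.317. Power at r = 0.31 is 78% by Fisher z and 80% by noncentral t. The stated 0.31 reproduces, but for raw correlations and not for this regression.

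**Assumed inputs.** The documents give neither the correlation of baseline HRSD with HRSD change (r_b) nor the SDs of speed change that go with one SD of baseline HRSD (q). I use r_b = -0.3, -0.5 and -0.6. With equal SDs at both visits, r_b = −√((1 − ρ)/2), so pre-post correlations ρ of 0.8, 0.5 and 0.3 give -0.316, -0.500 and -0.592. Baseline HRSD is assumed to correlate -0.3 with each baseline speed.

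**Precision, with q = 0.** Residual degrees of freedom are 76 − 6 = 70 as planned and 69 with baseline HRSD. If the two baseline speeds are related only through baseline HRSD, they explain R² = 2(0.09)/(1 + 0.09) = 0.165 of it. Then

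SE ratio = √[(1 − r_b²)/(1 − 0.165 r_b²)] × √(70/69).

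| r_b | SE ratio, formula | SE ratio, simulated (6,000 runs) | SE cut by adjusting |
|---|---|---|---|
| -0.3 | 0.968 | 0.967 | about 3% |
| -0.5 | 0.891 | 0.891 | about 11% |
| -0.6 | 0.831 | 0.832 | about 17% |

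Read the other way, the planned SE is 1/0.967, 1/0.891 and 1/0.832, or about 3%, 12% and 20%, above the adjusted one. If the baseline speeds carry no information on baseline HRSD, the ratio is √(1 − r_b²) × √(70/69), and the cuts are 4% at ρ = 0.8, 13% at 0.5 and 19% at 0.3.

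The gain shrinks if baseline spread is narrow. Take SD 4 at baseline, 6 at week 8 and ρ = 0.5 (all assumed). Covariance of baseline with change = 0.5 × 24 − 16 = −4; variance of change = 16 + 36 − 24 = 28; r_b = −4/(4 × 5.29) = −0.19. The SE ratio is √(1 − 0.036) × √(70/69) = 0.989, a gain of about 1%.

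**Bias, mechanism A: the observed baseline score predicts speed change.** 76 completers, 6,000 runs per setting, true slope zero. With q = 0, both models reject in about 5% of trials. With q = 0.2 to 0.3:

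| r_b | Planned model rejects | With baseline HRSD |
|---|---|---|
| -0.3 | 6.5–10% | about 5% |
| -0.5 | 11–20% | about 5% |
| -0.6 | 15–26% | about 5% |

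Repeat runs agreed, with upper values 1 to 3 points lower. The false slope is roughly r_b × q: at r_b = -0.5 and q = 0.3, −0.15 SD of HRSD change per SD of speed change. With q negative its sign reverses and a true effect is hidden. At q = -0.2 and r_b = -0.5, a moderate true slope that the adjusted model detects in about 64% of trials is detected in about 30% by the planned model.

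**Bias, mechanism B: a stable severity trait, measured with noise at both visits, drives speed change.** The trait cancels out of the change score, so the planned model is unbiased. Given a noisy baseline, however, a larger speed gain still signals a higher trait and hence a higher week 8 score. With ρ = 0.5, true slope zero and 3,000 runs:

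| SD of speed change per SD of trait | Planned model rejects | With baseline HRSD |
|---|---|---|
| 0.2 | 4.7% | 10% |
| 0.3 | 5.7% | 17% |
| 0.4 | 4.5% | 23% |

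Here the adjusted slope is biased against Hypothesis 2.

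**The case against.** The strongest objection is mechanism B. Aim 3.1 adjusts for baseline HRSD in comparing randomized groups, where adjustment gains precision without risking bias. Speed change is not randomized, so that argument carries over for precision but not for bias. A change-score model and a baseline-adjusted model can then disagree, and the documents do not say which mechanism applies. This stands, and it is why the unadjusted model should not simply be discarded.

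The precision gain also rests on assumed correlations, and the HRSD entry cap may narrow baseline spread. This stands for the size: the gain could be 1% rather than 17%. It does not make the omission useful.

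The confounding path is thinly supported. The Background section describes longer-term links between mood and gait. It does not say that baseline HRSD predicts 8-week speed change once treatment and both baseline speeds are held fixed. This stands too, so bias is a possibility and not a finding.

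A reader might infer that the planned model will manufacture support for Hypothesis 2. The documents do not support this: they fix neither the existence nor the sign of the path, and with no path the planned model keeps its 5% error rate.

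**Conclusion.** The omission is clear on the text, and its consequences are modest. The precision loss needs only that HRSD change depends on its baseline, as Aim 3.1's own adjustment anticipates. Its size, an SE cut of about 3% to 17% with a floor near 1%, rests on the assumed correlations. Bias is conditional: it needs the observed baseline score to predict speed change given treatment and baseline speeds, and it can favour or oppose the hypothesis.

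Two stronger readings should be resisted. One is that adding baseline HRSD restores a 5% error rate in general; that holds under mechanism A but not under B, where the adjusted model rejects in 10% to 23% of null trials. The other is that the trial's main result is in doubt. The Aim 3.1 treatment comparison already includes baseline HRSD and is untouched. The Aim 3.2 regression is a secondary, associational analysis, and it covers only the speed part of Hypothesis 2, since raclopride binding is not in it.

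**What to change.** In SAP Aim 3.2, add baseline HRSD to the covariates, so that HRSD change is regressed on treatment, processing and gait speed change, baseline processing and gait speed, and baseline HRSD. Pre-specify this as the main model for the speed part of Hypothesis 2.

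Keep the currently planned model, without baseline HRSD, as a stated sensitivity analysis. Say why: speed change is not randomized, and adjusting for a noisy baseline can itself bias the slope. If the two slopes differ materially, report both and treat the association as dependent on the mechanism assumed. Make the change before unblinding, so that the covariate set is not chosen on the results.

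The cost is one of about 70 residual degrees of freedom and one extra model. No new data are needed: the protocol already collects the 24-item HRSD at evaluation and weekly.
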